5.2.3 Inclusion of Women and Minorities

Both men and women and members of all races and ethnic groups are eligible for this trial.

5.2.4 Patient Recruitment

Patients will be contacted by phone via physician referrals and from investigator attendance at the weekly Pancreatic Multidisciplinary Conference. In addition, the schedule of Whipple surgeries will be requested on a weekly basis from the operating room schedulers. Patients eligible for the study will then be contacted by phone by the investigator.

5.2.5 Protocol and Drug Administration

This study will be conducted in accordance with the Sidney Kimmel Comprehensive Cancer Center's Coordinating Center Protocol.

5.2.6 Multicenter Guidelines

Protocol Chair

The Protocol Chair is responsible for performing the following tasks:

- Coordinating, developing, submitting, and obtaining approval for the protocol as well as its subsequent amendments.
- Assuring that all participating institutions are using the correct version of the protocol.
- Taking responsibility for the overall conduct of the study at all participating institutions and for monitoring the progress of the study.
- Reviewing and ensuring reporting of Serious Adverse Events (SAE) \Box Reviewing data from all sites.

Coordinating Center

The Coordinating Center is responsible for performing the following tasks:

• Ensuring that IRB approval has been obtained at each participating site prior to the first patient registration at that site, and maintaining copies of IRB approvals from each site.

- Managing central patient registration.
- Collecting and compiling data from each site.
- Establishing procedures for documentation, reporting, and submitting of AE's and SAE's to the Protocol Chair, and all applicable parties.
- Facilitating audits by securing selected source documents and research records from participating sites for audit, or by auditing at participating sites.

Participating Sites

Participating sites are responsible for performing the following tasks:

- Following the protocol as written, and the guidelines of Good Clinical Practice (GCP).
- Submitting data to the Coordinating Center.
- Registering all patients with the Coordinating Center by submitting patient registration form, and signed informed consent promptly.
- Providing sufficient experienced clinical and administrative staff and adequate facilities and equipment to conduct a collaborative trial according to the protocol.
- Maintaining regulatory binders on site and providing copies of all required documents to the Coordinating Center.
- Collecting and submitting data according to the schedule specified by the protocol.

5.2.7 Patient Registration

Prior to protocol enrollment and initiation of treatment, subjects must sign and date an IRB approved consent form. All patients must be registered centrally at the Sidney Kimmel Comprehensive Cancer Center.

To register a patient, sites must send the following documents to [name] at the Coordinating Center by email at

- Registration Form
- HIPAA authorization form (if separate from consent)
- Eligibility screening checklist
- Copy of all required screening tests.

The Coordinating Center will review the documents to confirm eligibility. To complete the registration process, the Coordinating Center will:

- assign a patient study number
- register the patient on the study with the Sidney Kimmel Comprehensive Cancer Center's Clinical Research Office
- E-mail the patient study number to the participating site.

5.2.8 Randomization

at

Subjects who are eligible to enroll in the study will be randomized in a 1:1 ratio to receive CC486 or observation. Subjects will be randomized through a computer program maintained by the study team.

- CC-486 (three 100 mg tablets on Days 1-21 every 28 days)
- Observation

The randomization will be balanced by using randomly permuted blocks and will be stratified by the following criteria:

• Positive lymph nodes at time of resection (N0 versus N1)

Approximately 55-75% of patients are expected to be node positive.^{10, 13, 40-42}

CC-486 will be packaged and designated for a patient upon randomization to Arm A. Subsequent bottles of study drug will be made available to patients as needed. Patient will receive one bottle of study drug with no more than 63 tablets in the bottle.

External sites will submit a patient enrollment log to the Coordinating Center monthly by email,

5.2.9 Dosage Dispensing and Administration

Treatment will be administered on an outpatient basis. Reported adverse events and potential risks are described in Section 6. Appropriate dose modifications are described in Section

No investigational or commercial agents or therapies other than those described below may be administered with the intent to treat the patient's malignancy.

5.2.9.1 Dispensing and Administration of CC-486

On Day 1 of each cycle, subjects in Arm A will be administered three tablets of 100 mg of CC486 in clinic with approximately 8 ounces (240mL) of room temperature water. CC-486 may be taken on an empty stomach or with food. Dosing can occur at any time during the morning after completing the required pre-dose assessments. Time of dose should be recorded in study documents. Anti-emetics can be administered per discretion of the investigator (per Section 5.4.1) on an as needed basis.

For each cycle, subjects in Arm A will take the three 100 mg tablets of CC-486 on days 1-21 of a 28 day cycle. On the first day of every cycle, subjects will be given a quantity of study drug for the dosing days at home. Subjects should be instructed to inspect each CC-486 tablet and only take tablets that are totally intact. Subjects should be instructed to return any doses not taken or

any tablet(s) found to be not totally intact to the study clinic on the first day of each cycle, beginning with Cycle 2. Subjects should be instructed to open the study medication packaging as close as possible to when they are going to take the study drug and record the time of study drug administration on a diary card (Appendix B). The diary card will be returned to clinic staff at the end of each cycle. On days when study drug is taken at home, subjects should be encouraged to ingest CC-486 with approximately 8 ounces (240mL) of room temperature water. CC-486 may be taken on an empty stomach or with food.

If a dose of CC-486 is missed, it should be taken as soon as possible on the same day. If it is missed for the entire day, it should not be made up. If the patient vomits after a dose is taken, no more subsequent tablets should be administered.

The cycle length is 4 weeks (28 days). Treatment with protocol therapy will continue until unacceptable toxicities or subject has visible disease progression on imaging. Further details per Sections 5 and 7.

If CC-486 is shipped directly to patients for the safety of patients and staff as part of COVID-19 precautions, a courier that monitors drug shipment conditions should be utilized. Study staff must call the patient to ensure that shipment was received in good condition at the patient's home, and instruct patient to keep and return all empty, partially empty, or full bottles/blisters to the site at next visit for drug reconciliation. This call, including verbal confirmation of receipt by the patient, should be properly documented in the medical record. If COVID-19 precautions prevent the return of used/unused study drug supplies to the site, then study staff must review the remaining pills during a telemedicine visit. Undelivered supplies should be returned to the clinical site.

5.2.10 Record of administration

Accurate records will be kept in the source documents of all drug administration (including prescribing and dosing). Subject diaries will be collected at the end of each cycle and at the discontinuation of treatment.

Review of remaining pills and pill diary may be reviewed during a telemedicine visit when drug is unable to be returned to study staff due to COVID-19 precautions. Copies of the pill diary may be submitted to study staff by phone, fax, email, or mychart.

5.3 Visit Schedule, Assessments, and Dose Modifications

Screening assessments and all on-study scheduled visits and assessments are outlined in Section 2 Table of Study Assessments and detailed below.

5.3.1 Screening and Pre-Study Assessments

Screening for enrollment in this clinical trial should include a record of prior medications and anti-cancer treatments, a record of concomitant medications and procedures, medical history, a physical examination, vital signs, weight, ECOG performance status (per Appendix A), pregnancy test, labs (CBC with differential, serum chemistry and hepatic panel, CA 19-9, PT, PTT), research labs, quality of life measures and lesion assessment with CT (per Section 7). All pre-study assessments should be done ≤ 28 days from Cycle 1 Day 1.

5.3.2 Initial Phase: Assessments, Dose Modifications, and Termination 5.3.2.1 Arm A for first cycle

Prior to receiving Cycle 1 Day 1 of CC-486, patients must undergo a physical examination including vital signs, weight, and ECOG performance status assessments, and labs including CBC with differential, serum chemistry and hepatic panel, CA 19-9, PT/PTT, and research blood, a record of concomitant medications and procedures, quality of life, and an assessment of adverse events. If screening assessments were done within 7 days of initiating Cycle 1 Day 1, these do not need to be repeated. Cycle 1 of CC-486 in Arm A can then be administered on schedule if treatment criteria are met.

5.3.2.2 Arm A for first 12 cycles

Arm A patients will be evaluated on Day 1 of every cycle with a physical examination, ECOG performance status, vital signs, weight, CBC with differential, research blood and serum chemistry and hepatic panel. Arm A patients will also complete an assessment of adverse events and reporting of current medications/procedures on Day 1 of every cycle.

Arm A patients will complete a CA 19-9, quality of life assessment and CT scan on Day 1 of every third cycle beginning at Cycle 4.

Arm A subjects will be evaluated for adverse events on Day 1 of each cycle with the NCI CTCAE v4.0 (http://ctep.info.nih.gov) used as a guide for the grading of severity. For Arm A patients, doses will be reduced for hematologic and other non-hematologic toxicities that can be attributed to the study drug. Dose adjustments are to be made according to the system showing the greatest degree of toxicity. When a dose reduction is required for Day 1 of any cycle, no dose re-escalation will be permitted for the duration of study treatment.

NOTE: Arm B patients will not be evaluated for adverse events as they do not receive the study agent.

Criteria to Initiate Treatment

In Arm A, a new course of treatment may begin on the scheduled Day 1 of a new cycle if:

- Absolute neutrophil count $\geq 1500/\text{mm}^3$
- Platelet count $\geq 100,000/\text{mm}^3$
- Serum creatinine levels < 2 mg/dL
- Serum bilirubin levels $\leq 1.5 \text{ mg/dL}$.
- AST (SGOT) and ALT (SGPT) \leq 2.5 x the institutional upper limit (ULN) of the normal range
- Any other drug-related adverse events that may have occurred must have resolved to < Grade 2 severity except grade 2 anorexia and any correctable metabolic abnormality.
- No evidence of visible disease recurrence on imaging (if indicated per Study Schedule, Section 2, to be done prior to cycles 4, 7, and 10)

If these conditions are not met on Day 1 of a new cycle, the subject will be evaluated weekly and a new cycle of treatment will not be initiated until the toxicity has resolved as described above utilizing the dose modifications as depicted below. If the study drug has to be held for > 28 days, study treatment will be discontinued.

5.3.2.3 Arm B for the first 12 cycles

Arm B patients will ideally be evaluated (or at the very least contacted by the study team) on Day 1 of every third cycle beginning with Cycle 4.

Patients are permitted to see their local oncologist, and CA19-9 and lesion assessments may be completed outside of the recommended 3 month window (Cycles 4, 7, and 10) at their oncologist's discretion.

Arm B patients will follow a similar schedule as patients in Follow-up, except for a Quality of Life assessment that will be performed.

Correlative blood draw is optional for Arm B patients. If Arm B patients wish, they may have research bloods drawn for correlative studies.

Arm B patients who opt to have research blood collected will have it collected on Day 1 of every third cycle (cycle 4, 7 and 10).

Below is the list of information that must be obtained from Arm B patients.

- Any further therapy received (records to be obtained)
- Subjective response on therapy (records to be obtained)
- Any CA 19-9 drawn (records to be obtained)
- Any imaging (images to be obtained)

Arm B patients will complete a CA 19-9, quality of life assessment and CT scan (or alternate imaging, if clinically indicated) quarterly (ideally).

Arm B patients who are not evaluated in person may have the Quality of Life assessment completed over the [contact] Dose Modification

Table 5.3.1: Arm A: Dose Modification Recommendations for CC-486 Phase
--

Toxicity	Grade	CC-486
Febrile Neutropenia	Grade 3 or 4	Hold until resolved and neutrophils \geq 1500/mm ³
		Restart study drug at 200 mg (two tablets, 33% dose reduction).
		If the same Grade 3 or 4 event recurs (i.e., third occurrence) despite CC-486 dose reduction to 200 mg, as described above, permanently discontinue study
Leukopenia and/or Neutropenia	Grade 2-3Hold dose until recovery to Grade ≤ 1 or baseline.Resume study drug at prior dose	
	Grade 4	Hold until resolved to \leq Grade 1
		Restart study drug at 200 mg (two tablets, 33% dose reduction).
		If the same Grade 4 event recurs (i.e., third occurrence) despite CC-486 dose reduction to 200 mg, as described above, permanently discontinue study drug.
Thrombocytopenia	Grade 1* or 2	Hold treatment until resolution to normal values.
	Grade 3 or 4	Hold until resolved and platelet count ≥100,000/mm ³ Restart study drug at 200 mg (two tablets, 33% dose reduction)
Diarrhea (unresponsive to maximum medical	Grade 1 or 2	Consider administering symptomatic remedies and/or start prophylaxis.
management)		No dose/schedule changes

Toxicity	Grade	CC-486	
	Grade 3 or 4	Hold until resolved to \leq Grade 1 Restart study drug at 200 mg (two tablets, 33% dose reduction).	
Nausea/Vomiting (unresponsive to maximum medical management)	Grade 1 or 2	Consider changing/adding antiemetic medication treatment No dose/schedule changes	
	Grade 3 or 4	Hold until resolved and neutrophils \geq 1000/mm3 Restart study drug at 200 mg (two tablets, 33% dose reduction).	

*Grade 1 thrombocytopenia: Platelet count < 100,000/mm³

Study drug should be stopped if grade 3 or 4 toxicity has occurred despite a dose reduction to 66% of original dose (200 mg of CC-486 in two 100 mg tablets).

If grade 3 or 4 toxicities require patients to stop treatment mid cycle, they can resume their cycle at the recommended decreased dose if the toxicities resolve to \leq Grade 1 within their 21 days of treatment (i.e. they would only continue treatment to complete their days 1-21 per the calendar, not to complete 21 days of taking the tablets). If their toxicities recover after their 21 days has completed, they will not take more tablets until they begin their next cycle.

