- ¹ If study assessment assessed within 7 days of Cycle 1, Day 1, they do not need to be repeated.
- ² Correlative blood sampling is optional for patients in Arm B except for at screening and at time of visible disease progression.
- ³ For patients assigned to Arm A, research blood will be collected for tumor methylation analysis and other correlative studies on Day 1 of *every* cycle.
- ⁴ For patients assigned to Arm B, research blood will be collected for tumor methylation analysis and other correlative studies at screening and/or Cycle 1 Day 1 and Day 1 of *every third* cycle beginning with Cycle 4 (Cycle 4, 7, 10).
- ⁵ Patients on Arm B can provide this information to study team member over the phone.
- ⁶ Patients on Arm B who opt not to participate in correlative blood sampling may be assessed by their local oncologist for all clinical, laboratory and imaging parameters.
- ⁷ If study assessment was completed within 7 days of noting visible disease progression, they do not need to be repeated.
- ⁸ For Arm A patients, if research blood was collected within one month, it does not need to be repeated. For Arm B patients, if research blood was collected within 3 months, it does not need to be repeated.
- ⁹ Please refer to Appendix A for definition of ECOG performance status.
- ¹⁰ Radiologic imaging of chest/abdomen/pelvis (CT preferred, abdominal/pelvis MRI will be performed for patients with CT contrast allergy) and any other imaging required per RECIST for the particular subject are required at baseline must be obtained within 4 weeks of initiation of therapy.
- ¹¹ Assessment for presence of visible disease will occur prior to every third cycle, beginning with Cycle 4 (Cycles 4, 7, 10). For each individual patient, the same imaging modality should be used at assessment as was used during screening.
- ¹² Obtain a urine or serum pregnancy test at screening no more than 7 days prior to dosing on Day 1.
- ¹³ Tumor biopsies will be obtained at the time of visible disease recurrence for all subjects. Location of biopsy can be primary tumor or site of metastatic disease, as determined by the treating oncologist. Tumor biopsy may be obtained within 4 weeks of visible disease progression or before first dose of chemotherapy, whichever occurs latest.
- ¹⁴ Completed only if FACIT data not collected at time of visible disease progression

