5.4 Discontinuation of Treatment: Arm A

In the absence of treatment delays due to adverse events, treatment with CC-486 may continue until one of the following criteria applies:

• Interruption of scheduled therapy for greater than four weeks,

- Intercurrent illness that prevents further administration of treatment,
- Adverse event(s) that, in the judgment of the Investigator, may cause severe or permanent harm or which rule out continuation of the treatment regimen
- For any grade 3 and 4 toxicity that recurs despite dose reduction
- Discontinuation of CC-486 for any reason,
- Treatment with other chemotherapeutic or investigational anti-neoplastic drugs,
- Subject decides to withdraw from the study,
- Suspected pregnancy or positive pregnancy, or
- General or specific changes in the subject's condition render the subject unacceptable for further treatment in the judgment of the investigator, or
- Disease recurrence on imaging, or
- Patient has completed one year of therapy with CC-486.

If the subject has visible disease recurrence on imaging or meets any of the aforementioned criteria for removal from study treatment, then the CC-486 or observation phase of this study will conclude and patient will enter the follow-up phase of the study, following the schedule of assessments as described in Section 5.4.2.9.

Mandatory research bloods and tumor biopsies will be obtained at the time of recurrence for both Arm A and Arm B subjects, per the method determined best per the investigator as outlined on the Study Calendar and in Section.

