7.1 Baseline imaging assessments

Baseline imaging assessment must occur within ≤ 28 days of initiation of the CC-486 /observation phase to document lack of visible disease on imaging as indicated in Section 2, Schedule of Study Assessments. Acceptable imaging modalities are described below and must include imaging of the chest, abdomen and pelvis. To be declared free of visible disease, there can be no evidence of measurable disease, as defined below, or presence of malignant effusions.

All effusions that can safely be diagnostically drained must be evaluated prior to enrolling to document lack of malignant cells via thoracentesis or paracentesis. Fluid that is non-specific or too small to drain is considered no visible disease. If there is a concern for bone metastasis or brain metastasis based on clinical symptoms, bone scan and/or brain MRI must be done to rule out metastatic disease prior to enrolling on this study. These scans do not need to be done in the absence of concerning clinical symptoms.

Imaging will be performed every 3 cycles while on the CC-486. Ideally, imaging will be performed every 3 cycles for patients on the observation arm, but ultimately imaging/lesion assessments will be performed at the patient or his/her oncologist's discretion. When patients have evidence of measurable disease, as defined below, they will then be classified as having "visible disease". If a lesion or effusion appears but is not confirmed to be disease until a later time point, the time noted for a patient to have "visible disease" should revert back to the time the lesion or effusion initially appeared. They will stop the CC-486 /observation phase and enter the follow up phase. Imaging assessment ideally should occur within ≤ 28 days of initiation of first-line chemotherapy. If there is a delay between initial documentation of visible disease and starting treatment, imaging may be repeated as indicated in Section 2, Schedule of Study Assessments to get a true baseline.

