11.3.3 Quality of life analysis

Quality of life will be assessed at screening and/or cycle 1 day 1 and then every 3 cycles thereafter (cycles 4, 7 and 10) using the Functional Assessment of Chronic Illness Therapy Hepatobiliary Cancer (FACIT-Hep) questionnaire. The hepatobiliary, general function, and subscale scores will

be will be graded according to the guidelines provided at http://www.facit.org. Summary statistics (e.g. means, medians, ranges) and graphical techniques (e.g. box-plots over time) will be used to summarize the patterns of scores over time and assess whether or not transformations are necessary. Comparisons of the differences in the change in scores over time between treatment groups will be performed using generalize estimating equations (GEE). Sensitivity analyses will be performed to assess the impact of missing data including best and worst case single imputation, multiple imputation. One issue when assessing quality of life is how to handle scores for individuals who have died. Some questionnaires (e.g. Stroke modified Rankin Score) include death as a value on the scale; however, this is not the case for the FACIT questionnaires. We will assess the impact of missing data due to death by assessing the worst category score for those who have died.

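### After CC-486 is stopped without recurrence, Arm A has no scheduled Cycle 4, 7 or 10 quality-of-life form, while recurrence-free Arm B patients continue to Cycle 10

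*Combined protocol and SAP*

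**What the plan says.** **Arm A.** Section 5.3.2.2 schedules a "quality of life assessment and CT scan on Day 1 of every third cycle beginning at Cycle 4". Section 5.4 lists what ends treatment, including "Discontinuation of CC-486 for any reason". When any listed criterion is met, "then the CC-486 or observation phase of this study will conclude and patient will enter the follow-up phase of the study". Schedule 2.2 for that phase covers new therapies, subjective response, CA 19-9, imaging and study-team contact. Neither it nor the list in Section 5.5 includes quality of life.

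**Arm B.** Section 5.3.2.3 states "Arm B patients will complete a CA 19-9, quality of life assessment and CT scan (or alternate imaging, if clinically indicated) quarterly (ideally"). The same section treats the questionnaire as the exception to a follow-up type of schedule: "Arm B patients will follow a similar schedule as patients in Follow-up, except for a Quality of Life assessment that will be performed". Footnote 5 of schedule 2.1 allows it by phone.

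**Other scheduled forms.** Schedule 2.1 marks quality of life at visible progression in both arms. It also marks it at the Arm A safety assessment 28 days after discontinuation, with footnote 14: "Completed only if FACIT data not collected at time of visible disease progression". Section 5.4.1 (End of Treatment) does not list it.

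**Analysis.** Section 11.3.3 names screening or Cycle 1, then Cycles 4, 7 and 10. It plans that "Comparisons of the differences in the change in scores over time between treatment groups will be performed" by GEE, with best-case, worst-case and multiple imputation as sensitivity analyses.

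**The concern.** The rule that decides who is still asked to fill in the form differs by arm. Recurrence ends routine collection in both arms. Toxicity, a hold of more than 28 days or a patient's own choice to stop the drug ends it in Arm A only, because Arm B has no drug to stop. At Cycles 4, 7 and 10, Arm A is thus reduced to recurrence-free patients who are still on drug, while Arm B holds all its recurrence-free patients.

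The synopsis gives showing that CC-486 is well tolerated as part of the trial's goal, and change in quality of life is a secondary endpoint. Adverse events are collected in Arm A only (Sections 5.3.2.2 and 6.1). FACT-Hep, which asks about nausea, diarrhea and bother from side effects (Appendix D), is therefore the only planned between-arm comparison of tolerability as patients experience it. If poor tolerators drop out of one arm's scheduled visits, that comparison can flatter the drug, and later analysis cannot recover forms that were never requested.

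**Working it through.** **1. What is scheduled after each event**

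| Event | Arm A | Arm B |
|---|---|---|
| Recurrence-free, on schedule | Cycles 4, 7, 10 | Cycles 4, 7, 10 (phone allowed) |
| Visible recurrence | form at progression, then follow-up with no form | the same |
| Stop of CC-486 without recurrence | one form at the 28-day safety visit, then follow-up with no row for it; possibly one at later progression | cannot occur |

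On recurrence, Section 7.1 treats both arms alike: "They will stop the CC-486 /observation phase and enter the follow up phase". The asymmetry is confined to the last row. Arm A forms are tied to Day 1 of a cycle, and Section 5.3.2.5 starts a delayed cycle when the dose is actually given, so a patient permanently off drug has no Cycle 4, 7 or 10 Day 1.

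**2. Size**

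The plan gives no quality-of-life sample size, completion rate or stopping rate, so there is no such figure to reproduce.

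Inputs from the documents: 30 patients per arm and a null median PFS of 6 months (11.3.4); an alternative of 9.84 months (11.3.6); 28-day cycles. Exponential PFS is an assumption, but it matches the plan's own power. With 24 months of accrual, 12 months of follow-up and 10% loss, 51.2 × 0.9 = 46.1 events. Then √46.1/2 × ln 1.64 − 0.842 = 0.838, and Φ(0.838) = 0.799, against the stated 80%.

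Assumed: a proportion q of 5%, 15% or 30% stops CC-486 without progression over 12 cycles (336 days), at a constant rate and independently of recurrence.

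Cycles 4, 7 and 10 Day 1 fall 84, 168 and 252 days after Cycle 1 Day 1, or 2.76, 5.52 and 8.28 months.

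- Forms due = 30 × exp(−ln 2 × t/6): 30 × 0.727 = 21.8; 30 × 0.529 = 15.9; 30 × 0.384 = 11.5. The sum is about 49.2.
- Fraction not yet stopped = (1 − q)^(days/336), with exponents 0.25, 0.50 and 0.75.

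| Assumed q | Cycle 4 | Cycle 7 | Cycle 10 | Total | Lost of 49.2 | Lost at Cycle 10 |
|---|---|---|---|---|---|---|
| 5% | 21.5 | 15.5 | 11.1 | 48.1 | 1.1 | 3.8% |
| 15% | 20.9 | 14.6 | 10.2 | 45.7 | 3.5 | 11.5% |
| 30% | 19.9 | 13.3 | 8.8 | 42.0 | 7.2 | 23.5% |

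At the alternative median of 9.84 months the forms due are 24.7 + 20.3 + 16.7 = 61.7. With q = 30% the loss is 24.7 × 0.085 + 20.3 × 0.163 + 16.7 × 0.235 = about 9.3.

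The schedule causes no loss for this reason in Arm B.

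**The case against.** **Collection does not simply end.** A reader might infer that quality-of-life data stop in Arm A as soon as the drug does. The schedule contradicts this: footnote 14 calls for a form at the safety visit in exactly the case of a stop without progression, and a form at progression is scheduled in both arms. This stands, and limits the point to the Cycle 4, 7 and 10 forms. But the safety form is a single score 28 days after the last dose, at a visit meant to check that toxicity has resolved. It is outside the time points in 11.3.3 and absent from 5.4.1.

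**The numbers could be made to look larger.** A reader might take 10-30% of 30 patients, three forms each, and reach 9-27 of 90 forms. That requires every stopper to stop before Cycle 4 and then remain recurrence-free to Cycle 10. Nor do the 15% and 30% grade 3/4 rates in 11.3.5 support such stopping rates, since the plan provides for holding and resuming at a reduced dose before permanent discontinuation.

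**The direction is not shown.** Scores may recover after stopping, so adding off-drug forms could raise Arm A's average. Not every stopper is a poor tolerator. This stands: a bias in favour of CC-486 is likely, not established.

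**The objective concerns quality of life on drug.** That is how it is worded, and on-drug scores serve it. Section 11.3.3 nevertheless compares the two groups over time, and that comparison rests on who is asked.

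**The analysis already plans for missing data, and names the cycles without tying them to drug.** Imputation is a sensitivity analysis only, and stopping the drug is not mentioned as a cause of missing forms. Multiple imputation would have very few off-drug Arm A scores to learn from, and best- and worst-case values only bound the answer. Nothing bars the safety and progression forms from the GEE, but nothing includes them.

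**Arm B is not assured complete.** Its timing is an ideal, often met through local oncologists. The contrast is between schedules, not achieved completeness.

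**Conclusion.** The concern holds in a limited form. Following a stop without progression, routine forms at the analysis time points cease in Arm A, while a recurrence-free Arm B patient remains scheduled for them. Missingness in the between-arm comparison therefore depends on arm and partly on tolerability.

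The expected loss is modest: about 1-7 of roughly 49 Arm A forms at the 6-month median, rising to about 9 of 62 at the 9.84-month median with 30% stopping. These figures rest on the assumed 5-30% stopping range, constant rates, independence of stopping and recurrence, and full completion otherwise. They do not credit the safety-visit form. The loss is small in number, but one-sided, selective and avoidable. The documents do not support saying that Arm A data end when the drug stops, or that the comparison is certain to favour CC-486.

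**What to change.** 1. Add a quality-of-life row to schedule 2.2: Arm A patients off CC-486 without visible recurrence complete FACT-Hep at Arm B's time points (nominal Cycles 4, 7 and 10, that is days 85, 169 and 253 from Cycle 1 Day 1) until recurrence. Extend the phone option of footnote 5 to them.
2. State in 11.3.3 that these forms and the safety-visit form enter the as-randomized comparison, using actual assessment dates. Show on-drug scores separately for the objective about quality of life on CC-486.
3. Reconcile footnote 14 of schedule 2.1, schedule 2.2, Section 5.4.1 and Section 11.3.3 on which forms are due after a stop.

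The cost is a short amendment and at most three phone questionnaires per early stopper, at three-monthly contacts already planned in schedule 2.2 and Section 5.5. No treatment rule changes. The drawback is that Arm A's as-randomized scores will mix on-drug and off-drug periods, which is why the separate on-drug display is needed.
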